# **12.6.3 Other Planned Analyses**

Descriptive characteristics of patients will be reported in tabular form along with the dates of trial opening and closing, indicating the total number of patients enrolled and accounting for all patients considered for entry (flow diagram). Patients found to be ineligible will be indicated along with their reasons for ineligibility and whether they received any study therapy. Of the included subjects, the number of patients who were evaluable for toxicity and response (secondary objectives, see section **12.2.2**) will be reported.

Drug administration by dose level will be reported in tables detailing the total number of patients treated, number of doses or cycles received at dose level, and the number of incomplete cycles, including brief descriptions of what happened in dose escalation if intermediate dose levels or deviations from study protocol resulted. Any dose holds, reductions, and delays, and permanent discontinuation of study treatments will be summarized with reasons for each. Finally, summaries of dose intensity will be estimated, including how many patients were able to receive each planned dose intensity of Venetoclax administered with Gemtuzumab Ozogamicin.

Tables of adverse effects displaying the worst grade by dose level will be reported, including columns or each grade and "any grade" adverse effects. Separate tables report hematological and non-hematological effects will be reported according to dose escalation.

Descriptive tables reporting frequencies and means or medians of scores of the EORTC QLQ-C30 and FACT-Fatigue questionnaire, two-minute walk test, and timed chair stand will be created for D0 (trial entry) and subsequent months of follow up. Generalized linear modeling of continuous scores or ordinal values accounting for correlation and repeated will be performed to determine differences between groups

and characteristics considered to be potential confounding factors. Given a threshold value indicating a substantial degree of the outcome (i.e., quality of life, fatigue and physical function), generalized estimating equation models with a binomial distribution and unstructured correlation covariance will be used to produce odds ratios (OR) and robust 95% CI for the relation of dose and clinical characteristics to each outcome.

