# **1.2** Investigational Treatment

# 1.2.1 Gemtuzumab Ozogamicin (GO)

GO consists of a humanized anti-CD33 monoclonal antibody linked to calicheamicin, a potent antitumor enediyne antibiotic. GO binds to CD33, an antigen expressed on the surface of more than 90% of AML blast cells. Binding of GO is followed by internalization and intracellular release of calicheamicin, leading to DNA damage and subsequent mitochondria-dependent apoptosis.

The original FDA approval for GO was based on phase II studies of 9 mg/m2 given on days 1 and 14 in 277 patients with AML in first relapse, where it showed good tolerability, an overall response rate (ORR = complete remission (CR) and complete response with incomplete platelet recovery (CRp)) of 26%, and a median relapse-free survival (RFS) of approximately 6 months in patients aged >60 yrs (review). To reduce the hematological and hepatic toxicities seen with this dose and schedule, a French Cooperative group performed a phase II trial of GO 3 mg/m^2 given on days 1, 4, and 7, in patients with relapsed AML (n = 57). The rationale for lower dosing was based on responses observed with doses of 1–4 mg/m2 in the initial phase 1 study of GO. The administration of fractionated doses of GO was derived from observations of rapid re-expression of CD33 on the cell surface after an initial exposure (review). The ORR was 33%, and median survival improved to 11 months, with a marked reduction in adverse effects (e.g., median duration of >grade 2 thrombocytopenia fell to 21 days).

In a randomized phase III Cooperative group trial this GO dosing and schedule was next combined with a standard AML chemotherapy regimen ("7+3") and compared to "7+3" alone—resulting in significant gains in 2 year event-free survival (EFS), overall survival (OS) and RFS, despite no difference in initial CR rates. These benefits were confirmed in a recent meta-analysis as extending to 6 years in AML patients with low or intermediate risk cytogenetics, suggesting addition of GO increases the eradication of LSC, particularly in more "mature" AML with CD33-expressing LSC (reviews).

Note that patients in CR or CRp after induction received two further consolidation cycles of Gemtuzumab Ozogamicin (3 mg/m^2 on day 1) according to their initial randomization, in combination with daunorubicin and cytarabine.

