# 2.1.2 Secondary Objectives

- Estimate the efficacy of the combination in achieving ORR after first two cycles (overall response rate includes CR/CRi).
- Estimate the efficacy of the combination in achieving anti-leukemic activity (CR/CRi/PR).
- Characterize any adverse effects of GO in combination with Venetoclax.
- Estimate the relapse-free, event-free and overall survival.
- Longitudinal quantitative assessment of the effects of therapy on quality of life (QOL), degree of fatigue, and physical function.

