# 12.6.2 Analysis Plans for Secondary Objectives

Descriptive characteristics of all adverse effects of GO in combination with Venetoclax (using CTCAE v5 criteria) will be reported; and the efficacy of the combination in achieving ORR (includes CR/CRi) and anti-leukemic activity (includes CR/CRi/PR), as defined by the revised IWG criteria), RFS, EFS, and OS in subjects. The effects of therapy on quality of life, fatigue, and physical function at D0 (trial entry) and the end of every other month for 1 year (see section 8.1) will be reported and analyzed using generalized linear modeling.

All time-to-event outcomes (e.g. survival) will be calculated using Kaplan Meier methods and exploratory log-rank tests will be used to compare treatment effect between groups based on genomic MRD, CD33 DNA polymorphisms, BH3 profiling and anti-apoptosis protein levels in PB MBCs at presentation and after 1 week of Venetoclax.

*Sample size permitting:* Hazard ratios (HR) and 95% CIs will be produced. Time-to-event outcomes with a competing or semi-competing risk (e.g. CIR) will be analyzed using cumulative incidence curves and exploratory comparisons between arms will be made using Grey's test. Rate ratios and 95% CIs will be presented. Chi squared tests will be used to assess the treatment effect between cohorts for all categorical variables and t-tests or Mann Whitney tests will be applied for continuous measures as appropriate.

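### The quality-of-life tables in section 12.6.3 give unpaired scores at D0 and at later months with no rule for deaths or missed assessments, so attrition can make later scores look better than they are

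*Combined protocol and SAP*

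**What the plan says.** Section 2.1.2 lists as a secondary objective "Longitudinal quantitative assessment of the effects of therapy on quality of life (QOL), degree of fatigue, and physical function". The synopsis lists quality of life as exploratory.

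Three analyses are described:

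- **Tables (12.6.3).** "Descriptive tables reporting frequencies and means or medians of scores of the EORTC QLQ-C30 and FACT-Fatigue questionnaire", with the two-minute walk test and chair stands, "will be created for D0 (trial entry) and subsequent months of follow up". Section 12.6.2 sets the times as "at D0 (trial entry) and the end of every other month for 1 year".
- **Repeated-measures model (12.6.3).** "Generalized linear modeling of continuous scores or ordinal values accounting for correlation and repeated will be performed to determine differences between groups". Section 12.6.2 likewise names generalized linear modeling for these outcomes.
- **Threshold model (12.6.3).** For a dichotomised outcome, "generalized estimating equation models with a binomial distribution and unstructured correlation covariance", relating dose and clinical characteristics to the outcome.

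Neither section defines an analysis set for these outcomes, a change from baseline, a missing-data assumption or a treatment of death. Section 12.5 keeps patients who die before re-evaluation in the efficacy analysis, but quality of life has no counterpart. The only mention of missing data is the data-entry check in section 14.3.

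**The concern.** A column of D0 scores followed by columns for later months invites the reader to look along the row and see change over time. The columns do not hold the same patients. If those who leave had worse scores at entry, the later columns rise even when nobody improves.

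Section 1.3 hopes the combination will prolong survival and keep or improve quality of life. A table that drifts upward through attrition could be read as support for that hope, and one that stays flat could hide a decline. No dose decision depends on these data, so what is at stake is the interpretation of a secondary objective.

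**Working it through.** The plan states no effect size, SD or dropout rate for these outcomes, so there is no figure of its own to reproduce.

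**Inputs from the documents**
- Total N of 15 to 24 (synopsis; 9 + 6 = 15 and 18 + 6 = 24).
- Fractionated GO in relapsed AML: "median survival improved to 11 months" (section 1.2.1).
- Assessments at D0 and every other month to month 12, which makes 7 time points (section 12.6.2).

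**Assumptions, not in the documents**
- Exponential survival, with a 6-month median as a less favourable case.
- Correlation rho between D0 score and survival of 0.2 to 0.5, with 0 as the reference.
- Higher scores mean a better state. Results are in SD units of the score.

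**Step 1: who remains.** S(t) = 0.5^(t/median). With an 11-month median, S(12) = 0.5^(12/11) = 0.469, which is 7.0 of 15 or 11.3 of 24 patients. With a 6-month median, S(12) = 0.25, which is 3.8 of 15 or 6.0 of 24.

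**Step 2: shift with no true change.** Under a normal copula, the mean D0 score of survivors minus that of everyone is rho × φ(z)/S, with z = Φ⁻¹(1 − S).
- Median 11 months: z = 0.077 and φ(z) = 0.398, so the ratio is 0.398/0.469 = 0.847. The shift is 0.17, 0.25 and 0.42 SD for rho = 0.2, 0.3 and 0.5.
- Median 6 months: 0.318/0.25 = 1.271. The shift is 0.25, 0.38 and 0.64 SD.
- rho = 0: the shift is 0 in both cases.

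**Step 3: allow scores to vary within patients.** If later scores correlate 0.7 with D0 and survival is linked only through D0, the 11-month shifts are multiplied by 0.7: 0.12, 0.18 and 0.30 SD. Steps 2 and 3 together give the range of about 0.1 to 0.4 SD. For an assumed scale SD of 20 to 25 points, that is from 0.12 × 20 = 2.4 to 0.42 × 25 = 10.6 points.

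**Step 4: add a true decline.** This is a separate large-sample simulation with an 11-month median and within-patient correlation 0.7, where death is driven by the patient's stable underlying score. The cells show month-12 mean minus D0 mean, as the planned tables would display it.

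| True change (SD) | No link | Hazard ratio 1.5 per SD worse | Hazard ratio 2 per SD worse |
|---|---|---|---|
| 0 | 0.00 | +0.24 | +0.37 |
| −0.30 | −0.30 | −0.06 | +0.07 |
| −0.60 | −0.60 | −0.36 | −0.23 |

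The paired change among survivors recovered the true value in every cell. It is not exact in every set-up. In step 3 with rho = 0.3 it would show (0.7 − 1) × 0.254 = −0.08 SD through regression to the mean. That is still closer to the true zero than the unpaired +0.18.

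**Step 5: does the choice of model matter?** With hazard ratio 2 and a true decline of 0.48 SD by month 12:
- unpaired means showed −0.02;
- a GEE on the continuous score with independence working correlation showed −0.01;
- a random-intercept mixed model showed −0.42, or −0.35 when slopes also varied and drove death.

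The independence GEE is not the structure the plan names. An unstructured correlation may reduce the shift, but 7 time points need 7 × 6/2 = 21 correlations from 15 to 24 patients.

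**The case against.** The strongest reply has four parts.

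- **A repeated-measures model for continuous scores is already planned**, and a suitable one removes most of the shift (step 5). This stands as a limit on the point. A reader might infer that quality of life rests on tables and GEE alone, but the GEE applies only to the thresholded outcome. What remains is that the continuous-score model has no named estimation method and is aimed at differences between groups, not at change from D0.
- **No comparison of D0 with later months is stated.** A reader might infer that the plan sets all entrants against survivors, so that deaths will appear as stable or improving quality of life. The documents do not support that. They specify tables and no contrast between months, and they are silent on the analysis set. The mismatch of patients is the default result of that silence. The direction and size depend on a link between score and survival, which the cited median survival does not establish.
- **The shift is small against chance.** At rho = 0.3 and an 11-month median it is 0.25 SD, with a chance SD of 0.30 at N = 15 and 0.23 at N = 24. With later scores correlating 0.7 with D0 it is 0.18 SD against 0.36 and 0.28. This stands: one trial of this size could hardly separate the bias from noise. The bias nevertheless has a predictable direction and can be reduced at almost no cost.
- **Scores while alive, read beside overall survival, are a legitimate target.** This also stands. Counting death as quality of life not maintained answers a different question and is not a correction.

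The 75-day median time to relapse in section 1.2.2 should not be used as evidence of lost data. The study calendar continues these assessments through long-term follow-up, which section 7.2 runs for 6 months after progression. That continued collection may capture decline before death.

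**Conclusion.** The point holds as a gap in specification with a conditional bias. The planned tables are unpaired and nothing says how deaths or missed assessments enter. At the cited 11-month median, about half the D0 patients would be dead by month 12. If worse scores go with earlier death or dropout, the tables shift toward better scores by about 0.1 to 0.4 SD at month 12 with no true change, under assumed correlations of 0.2 to 0.5. The shift is zero without such a link and larger if survival is shorter.

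A true decline would be understated. A small one could vanish, while a steep one would still show as a decline. The correlations, hazard ratios, score SD, exponential form and 6-month median are assumptions. The primary objective and dose selection are unaffected, so this is an inexpensive improvement to the reporting of a secondary objective.

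**What to change.** **In 12.6.3:** report each later month as change from the patient's own D0 value, with the D0 mean of the same patients beside it. List for each month the numbers assessed, alive but not assessed, and dead.

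**In 12.6.2 and 12.6.3:** state that the continuous-score model is a likelihood-based mixed model with time as a factor, that it estimates change from D0, and that the result describes patients while alive and is read alongside overall survival.

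**Optional:** the proportion of all treated patients alive with a score no worse than baseline, labelled as a supplementary summary with its own target.

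The cost is analysis-plan wording and a few table columns, using data already collected. The quality-of-life figures may look less favourable.

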# PLEASE EMAIL COMPLETED FORM TO BIG TEN CRC ADMINISTRATIVE HEADQUARTERS

# **SYNOPSIS**

TITLE	Phase Ib study of the safety and efficacy of Gemtuzumab Ozogamicin (GO) and Venetoclax in patients with relapsed or refractory CD33+ acute myeloid leukemia					
PHASE	Ib					
OBJECTIVES	Primary Objective: To assess the maximum tolerated dose of Venetoclax when administered with Gemtuzumab Ozogamicin (GO) in patients with AML.					
	Secondary Objectives: To assess the efficacy of this combination in achieving overall response rate (ORR) and anti-leukemic activity; characterize any adverse effects of GO in combination with Venetoclax; and estimate the relapse-free, event-free and overall survival.					
	Exploratory Objectives: To assess the effects of therapy on quality of life; assess genomic minimal residual disease (MRD) to determine the kinetics of response and association with relapse-free survival.					
STUDY DESIGN	Dose-escalation study (Cohorts 1-3) to determine whether there is a dose- limiting toxicity.					
KEY ELIGIBILITY CRITERIA	Eligible patients, 18–75 yrs, will have relapsed/refractory AML, as defined by the World Health Organization classification; ECOG Performance score 0-2; adequate organ function; and do not meet exclusion criteria including WBC >25 × 10  /L (hydroxyurea permitted to decrease WBC count), unresolved ≥grade 2 clinically significant nonhematologic toxicities from prior anticancer therapy or unresolved ≥grade 2 DIC, other active malignancy within 1 year before study entry, major organ dysfunction, active infections, or pregnancy or breastfeeding.					
STATISTICAL CONSIDERATIONS	Standard 3+3 design					
TOTAL NUMBER OF SUBJECTS	N = 15-24 (n = 9-18, plus 6).					
ESTIMATED ENROLLMENT PERIOD	18 months					
ESTIMATED STUDY DURATION	30 months					

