# 5.1 Dose Escalation Rules

- Three to six subjects will initially be enrolled at dose level 1. If none of the 3 subjects experience a dose limiting toxicity (DLT) during the first cycle of therapy, an additional three subjects will be enrolled at dose level 2. If none of the 3 subjects at dose level 2 experience a dose limiting toxicity (DLT), an additional three subjects will be enrolled at dose level 3. If all subjects in dose level 3 complete the first cycle of therapy without DLT, 3 more subjects will be enrolled into dose level 3 to ensure only 0-1 of 6 subjects have a DLT. There will be no further escalation beyond dose level 3.
- Alternatively, if 1 of the first 3 subjects within any given dose cohort experiences a DLT, an additional 3 subjects will be enrolled at that dose level. If only 1 of the total 6 subjects in a dose level experience a DLT, the study will proceed to the next dose level as planned. If 2 of the total 6 subjects in any given dose cohort experience a DLT, the next lower dose level will be explored and considered the maximum tolerated dose (MTD) if no more than 1 of 6 subjects experience a DLT. If this occurs in cohort 1, the dose will be decreased to cohort -1 and if 2 or more DLTs are reached in dose level -1, the study will be put on hold and a protocol amendment will be considered. [see Section 6.4 for "Stopping Rules"]
- The MTD for Venetoclax in combination with Gemtuzumab Ozogamicin is defined as the dose level at which fewer than 33% of subjects experience a dose limiting toxicity (DLT), and specifically is the dose level at which less than 2 out of 6 subjects experience DLT. That dose will be the recommended Phase II dose (RP2D).
- Once the RP2D has been identified, we will expand this cohort to include an additional six patients to further evaluate the efficacy and safety profile of the RP2D.

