10: Whole blood to be collected pre-treatment, Cycle 1 Day +3 ( $\pm 1$  day), end of induction, end of consolidation, pre-treatment cycle 7 day 1 (i.e.  $\sim 6$  mo), pre-treatment cycle 13 day 1 (i.e.  $\sim 12$  mo), and relapse. See section 8. See Correlative Laboratory Manual (CLM) for collection, labeling, processing, and shipping instructions.

11: Bone marrow aspirate to be collected pre-treatment, end of induction, end of consolidation, pre-treatment cycle 7 day 1 (i.e.  $\sim$ 6 mo), pre-treatment cycle 13 day 1 (i.e.  $\sim$ 12 mo), and relapse. See CLM for collection, labeling, processing, and shipping instructions. Left-over samples will be banked for potential future studies, with patient consent. See section 8.

12: Pre-treatment evaluation includes buccal swab, whole blood collection, QOL (QLQ-C30, FACT-Fatigue), walk test, and chair stands. Pre-treatment bone marrow aspirate will be collected at screening. Aspirate collection for correlative studies is required prior to therapy.

13: QOL (QLQ-C30, FACT-Fatigue), walk test and chair stands to be performed pre-treatment, at the end of consolidation, every other cycle starting with Cycle 4 and throughout long term follow up.

14: Whole Blood, Serum and Plasma for banking to be collected pre-treatment, end of induction, end of consolidation, pre-treatment cycle 7 day 1 (i.e. ~6 mo), pre-treatment cycle 13 day 1 (i.e. ~12 mo), and relapse. See CLM for collection, labeling, processing, and shipping instructions. 15: It is suggested that patients should not receive HSCT conditioning within 2-3 months of last Gemtuzumab dose and that total body irradiation (TBI)/ total marrow irradiation (TMI) as part of a HSCT conditioning regimen be avoided, if possible, per discretion of the site PI.

09JUN2022

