# **12.2.2 Definition of Secondary Endpoints**

- Overall response rate (CR/CRi), as defined by the revised IWG criteria. See Section 9.1.
- Anti-leukemic activity (CR/CRi/PR), as defined by the revised IWG criteria. See Section 9.1.
- Adverse effects will be characterized using the CTCAE v5 criteria.
- Relapse-free survival (RFS), event-free survival (EFS, and overall survival (OS). See Section 9.2

• The European Organization for the Research and Treatment of Cancer 30 item questionnaire (EORTC QLQ-C30), The Functional Assessment of Cancer Therapy Fatigue (FACT-Fatigue) questionnaire, two-minute walk test, and timed chair stands will be performed at trial entry and every other month for 1 year.

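### The thresholded quality-of-life GEE in 12.6.3 pairs unstructured correlation with robust intervals in 15-24 patients and names no small-sample correction or fallback, so its intervals under-cover and with attrition it may not fit

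*Combined protocol and SAP*

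**What the plan says.** Section 12.6.3 of the combined protocol and SAP plans three analyses of the quality-of-life and function measures: descriptive tables at each time, a repeated-measures generalized linear model of the scores, and, where a threshold is given, a binary model. For the last, "generalized estimating equation models with a binomial distribution and unstructured correlation covariance will be used to produce odds ratios (OR) and robust 95% CI", relating dose and clinical characteristics to each outcome. The only cut-off in the documents is for severe fatigue (a score below 30, Appendix V).

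The plan does recognise that small numbers limit modelling, but the proviso to that effect opens the paragraph of 12.6.2 that begins "Hazard ratios (HR) and 95% CIs will be produced". That paragraph goes on to cumulative incidence, rate ratios and simple group tests. It does not reach 12.6.3.

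On timing, 12.2.2 says the questionnaires, "two-minute walk test, and timed chair stands will be performed at trial entry and every other month for 1 year". Note 13 of the study calendar (section 7) has them before treatment, at the end of consolidation, and "every other cycle starting with Cycle 4 and throughout long term follow up". On size, the synopsis gives "N = 15-24 (n = 9-18, plus 6"; section 12.3 gives 18-24 with the same bracket.

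**The concern.** An unstructured working correlation estimates a separate correlation for every pair of visits. With about as many correlations as patients, the estimated matrix is unstable, and missing visits can leave it not positive definite, so that no usable fit results. Separately, the ordinary robust (sandwich) variance is biased low when there are few patients, so its intervals are too short.

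At stake is the dose odds ratio and its 95% interval for secondary endpoints. An interval that is too short can make a chance association with dose look real. If the model does not fit, the choice of what to report instead would be made with the results in view, because 12.6.3 does not designate either of its other two analyses as the fallback.

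**Working it through.** **Sample size and allocation.** The synopsis range reproduces: 3×3 + 6 = 15 and 3×6 + 6 = 24. The lower bound of 18 in 12.3 does not follow from its own bracket (9 + 6 = 15), but it does follow from section 5.1. If the first three patients at level 3 have no DLT, "3 more subjects will be enrolled into dose level 3 to ensure only 0-1 of 6 subjects have a DLT", and then "we will expand this cohort to include an additional six patients", so 3 + 3 + 6 + 6 = 18. If a level proves too toxic, "the next lower dose level will be explored and considered the maximum tolerated dose (MTD) if no more than 1 of 6 subjects" have a DLT. Assuming a level closes once two of its first three patients have a DLT, this gives 3/12/3 = 18, or 12/3 = 15 with two levels. The point holds at either lower bound.

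**Correlations.** Entry plus months 2, 4, 6, 8, 10 and 12 is 7 assessments. The calendar also gives 7 within the year (pre-treatment, end of cycle 2, cycles 4, 6, 8, 10, 12). Correlations: 7×6/2 = 21, or 6×5/2 = 15 if baseline is a covariate.

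**Attrition (assumed).** Losses of 5%, 10% and 20% per visit leave 0.95^6 = 74%, 0.9^6 = 53% and 0.8^6 = 26% at the last visit. At 10%, the patients expected to have all seven visits number 24×0.531 = 12.8, 18×0.531 = 9.6 and 15×0.531 = 8.0. As a rough anchor, section 1.2.1 reports median survival of 11 months on fractionated GO; if exponential, 0.5^(12/11) = 47% are alive at 12 months.

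**Simulation A** (statsmodels binomial GEE; outcome probability 0.5; latent exchangeable correlation 0.5; linear dose plus one binary characteristic, both with no effect). Failure means not converged or a coefficient above 10 in absolute value; coverage is among usable fits; miss ratio = (1 − coverage)/0.05. Seven visits, complete data, 1,000 runs:

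| Allocation (N) | Unstructured fails | Coverage, unstructured robust | Miss ratio | Coverage, exchangeable robust | Coverage, exchangeable corrected, t(N−3) |
|---|---|---|---|---|---|
| 6/6/12 (24) | 0.1% | 84.5% | 3.1 | 89.4% | 94.4% |
| 3/3/12 (18) | 5.2% | 81.2% | 3.8 | 89.5% | 97.4% |
| 3/12/3 (18) | 7.3% | 77.0% | 4.6 | 87.2% | 96.2% |
| 12/3 (15) | 20.3% | 74.7% | 5.1 | 84.5% | 96.4% |

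With attrition (500 runs at 5%, 1,000 at 10%, 300 at 20%):

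| Allocation | Fails at 5% | Fails at 10% | Fails at 20% | Coverage of usable fits at 10% |
|---|---|---|---|---|
| 6/6/12 | 12.0% | 38.2% | 73.3% | 88.7% |
| 3/3/12 | 40.0% | 66.1% | 85.0% | 79.4% |
| 3/12/3 | not run | 67.2% | not run | 76.8% |
| 12/3 | 59.0% | 75.5% | 89.0% | 78.4% |

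At 10% loss the corrected exchangeable model covers 96.2-97.7% and fails in at most 1.9% of trials.

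Sensitivity, in the order 6/6/12, 3/3/12, 12/3:
- Correlation 0.3, complete data: unstructured coverage 85.8%, 78.0%, 69.4%; corrected 96.3%, 96.4%, 95.3%.
- Six visits, complete data: unstructured 88.4%, 80.9%, 81.2%; corrected 95.6-96.6%.

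The extremes give the miss-rate range: (1 − 0.887)/0.05 = 2.3 and (1 − 0.694)/0.05 = 6.1.

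**Simulation B** (separate code, time added to the model, 1,500 runs per scenario; allocations 6/6/12, 3/3/12 and, for the synopsis minimum, 3/3/9). A working correlation that is not positive definite counts as failure. With 60% retained at 12 months, failure is 38%, 60% and 73% at N=24, 18 and 15 for outcome prevalence 0.5, and 63%, 77% and 82% for prevalence 0.25. Across all retention levels (100% down to 20%), unstructured coverage is 79-88%, 72-85% and 71-81%. Exchangeable with the Mancl-DeRouen variance and t(N−4) covers 96-98%, with 0-4% failing. Simplifying the correlation without correcting the variance leaves 85-93%.

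**The case against.** Several parts of the case on the other side stand.

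- **Attrition.** A reader might infer that coming off study or relapsing ends quality-of-life collection. The documents do not support that: section 4 requires patients who stop treatment to be followed under 7.2, and calendar note 13 continues these measures in follow-up. Losses remain from death and from the 6-month limits in 7.2. For example, a patient progressing at month 2 is followed to about month 8, short of months 10 and 12. Telephone follow-up can yield questionnaires but not a walk test or chair stands.
- **Fit.** A reader might also infer that the model cannot be fitted in this trial. At N=24 with little loss it usually can: 0.1% failure with complete data and 12% at 5% loss in simulation A. Simulation B's stricter definition gives 9% with complete data at prevalence 0.5, and 36% at 0.25. Some packages return an estimate from an ill-conditioned matrix, so the percentages are not portable.
- **Silence, not error.** A robust interval does not exclude a corrected sandwich variance; the plan simply does not say which is meant. The under-coverage applies to the ordinary one.
- **Something would still be reported.** The descriptive tables and the score model are already planned. What is missing is a statement that they stand in for this model.
- **Choice of remedy.** It is partly preference: an independence working correlation with the same correction covers 96-99% in simulation B.

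None of this removes the under-coverage, which does not depend on attrition.

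**Conclusion.** The concern holds as a minor point of analysis choice. At about 10% loss per visit the specified model fails to fit in roughly 40% of trials at N=24 and 60-75% at N=15-18. Where it fits with the ordinary sandwich variance, the nominal 95% interval for dose covers about 70-89%, so it misses roughly 2 to 6 times as often as stated, depending on N, allocation, correlation and attrition.

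Attrition, outcome prevalence, within-patient correlation and the number of covariates are all assumed, because the documents give none of them. Confidence is high in the direction and lower in the exact failure rates. The worst coverage figures come from 12/3, where three patients make up one dose group and a dose odds ratio says little under any method.

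It would be wrong to read this as casting doubt on the trial's dose conclusion. The model is supplementary and conditional on a threshold, no trial decision rests on it, and neither the DLT/MTD conclusion nor the continuous-score model is affected.

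**What to change.** In 12.6.3, replace *unstructured correlation covariance* with *exchangeable working correlation*, and add: *Robust CIs use the Mancl-DeRouen small-sample corrected sandwich variance with t quantiles (patients minus regression parameters); if the model does not converge, the outcome is reported by the planned descriptive tables only.*

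Both parts are needed. The simpler correlation deals with most of the fitting failures, and the corrected variance deals with the coverage, which becomes about 94-98%.

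The cost is SAP wording; the data are the same and the software is standard. With complete data the log-odds-ratio interval for dose becomes about 1.3 times as wide at N=24, 1.6-1.7 times at N=18 and 1.9 times at N=15, and it tends to be slightly conservative.
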